7.7. Secondary analyses

To account for multiple testing the alpha level for secondary analyses will be set at $p = 0.01$.

Alternative measures of SEP

[figure not shown]
The main analyses will be repeated using alternative measures of SEP to investigate whether different measures lead to the same pattern of results. Highest educational qualification will be substituted by 1/ equivalised income, and 2/ SSS.

Moderated mediation analyses

[figure not shown]
We will report and compare the measures of inhibition, working memory, healthiness and weight control motivation in food choices overall and for participants of lower vs. higher education level using means, standard deviations and t-tests.

If the main analyses suggest that highest educational qualification moderates the effect of labelling intervention (i.e., the labelling intervention*highest educational qualification is significant), moderated mediation analyses will be performed in order to explain the different effect of labelling intervention in participants of lower vs. higher education level. We will test as mediators the measures of inhibition, working memory, healthiness and weight control motivation in food choices only if we find individual differences on these measures between participants of lower and higher education level. Moderated mediation analyses will examine the extent to which they mediate the effect of highest educational qualification on self-served energy in each labelling condition (kcal labelling, PACE labelling, kcal and PACE labelling, no labelling).

Conceptual diagram:

Statistical diagram:

Conditional indirect effect of highest educational qualification on self-served energy through a mediator M will be calculated as $a * (b_1 + b_2 * \text{labelling})$.

The moderated mediation will be tested by estimating the conditional indirect effect of highest educational qualification through M for kcal labelling, PACE labelling, kcal and PACE labelling, no labelling conditions and testing the conditional indirect effect for those conditions using bias-corrected bootstrap. We will use the PROCESS macro (Model 15) on SAS version 9.3 that provides asymmetric bias-corrected bootstrap confidence intervals for inference about the conditional indirect effects using 5,000 bootstrap samples [37]. Moderated mediation will be tested by determining whether or not the confidence interval for the difference between conditional indirect effects for kcal labelling, PACE labelling, kcal and PACE labelling versus no labelling contains zero.

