2. OBJECTIVES, OUTCOMES MEASURES AND HYPOTHESES

OBJECTIVES	OUTCOME MEASURES	HYPOTHESES

Primary objective
 
To investigate the effect of labelling (kcal or PACE) on the total self-served energy among participants of lower and higher SEP.
	
Total self-served energy in kcal from hypothetical meals
	
Labelling (kcal or PACE) will influence the size of self-served portion and result in reduced total self-served energy among both participants of lower and higher SEP.
 
Kcal and PACE labelling will exert a stronger effect on self-served energy among participants of higher compared to lower SEP.

		PACE labelling will exert a stronger effect on self-served energy than kcal labelling.
Secondary objectives To investigate the psychological processes that may explain the different effect of the intervention and whether health motivation and physical activity level mediate the differential effect of labelling (kcal or PACE) on total self-served energy among participants of lower and higher SEP.	Executive function (tasks) Health motivation in food choices (questionnaire)	Participants of higher SEP will have better executive function than participants of lower SEP, which will moderate the relationship between SEP and the effect of energy/PACE labelling on the total energy of the selected meal. Kcal/PACE labelling will exert a stronger effect on self-served energy among participants of higher SEP because they will be more motivated by health in their food choices than participants of lower SEP.

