5.5. Measure of physical activity level

The **International Physical Activity Questionnaire – Short Version** (IPAQ-SF) will be used to assess the physical activity level. The IPAQ-SF includes 7 items and records the activity of four intensity levels: 1) vigorous-intensity activity such as aerobics, 2) moderate-intensity activity such as leisure cycling, 3) walking, and 4) sitting [25]. Although the original authors recommended to ask about the last 7 days of recalled physical activity, due to the context in which this study will be run, i.e., self-isolation of UK population due to COVID-19 propagation preventive measures, we will ask about a usual week of recalled physical activity: number of days per week and how much time per day a participant usually does each of the four types of activity.

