7.3. Participant's characteristics

We will report the baseline characteristics overall and for participants of lower and higher education including gender, age, ethnic group, employment status, highest educational qualification, years in higher education, equivalised household income, subjective socioeconomic status, BMI, dieting status and physical activity in MET-minutes for vigorous-intensity activity, moderate-intensity activity, walking and in total. Continuous variables will be summarised using means and standard deviations and differences between the two groups will be tested using t-tests. Categorical variables will be summarised using counts and percentages and differences between the two groups will be tested using Chi-square tests.

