7.8. Exploratory analyses

To account for multiple testing the alpha level for exploratory analyses will be set at $p = 0.001$.

Analysis of potential moderators of the effect of the labelling intervention

We will explore if the other variables we will measure could individually moderate the effect of the labelling intervention on self-served energy independently of SEP. We will substitute highest educational qualification in the main analyses by measures of inhibition, working memory, healthiness and weight control motivation in food choices, physical activity in MET-minutes for walking and in total.

Debriefing questionnaire

Answers to all the items of the debriefing questionnaire will be described as mean \pm SD overall and for participants of lower and higher education. Differences between the two groups will be tested using t-tests. Two ANOVAs will be run to test the effect of the labelling intervention and of highest educational qualification on the first two items: kcal influence and PACE influence.

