In a previous study we conducted at virtual fast food restaurants [40], we found small-to-medium correlation between level of education and healthiness motivation ($r=0.17$) and small-to-medium correlation between healthiness motivation and kcal ordered ($r=-0.25$). Because evidence of a relationship between SEP and physical activity is mixed [41], we hypothesize small-to-medium correlation. Empirical estimates of sample sizes needed for 0.8 power in mediation analyses indicate that samples of ≈ 380 are sufficient to detect mediation through pathways that are small and small-to-medium in statistical size using bias-corrected bootstrap tests [42]. Thus, a sample of 1,600 participants (i.e., 400 per experimental condition) would allow for adequate power in our planned moderated mediation analysis.

We will recruit a sample of 1,800 participants (who consent to take part in the study) to account for potential data loss due to dropouts and failed quality controls (approx. 10%) resulting in a minimum sample of 1,600 participants for analyses. However, if we experience a greater loss of data than

expected, we will continue to recruit participants until we achieve the required sample size of 1,600 participants.

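### Physical activity is named as a mediator in the secondary objective, but no planned analysis tests it as one

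*Combined protocol and SAP*

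**What the plan says.** **Where physical activity is treated as a mediator.** In section 2 the secondary objective asks "whether health motivation and physical activity level mediate the differential effect of labelling (kcal or PACE"), the outcome being self-served energy and the contrast being lower against higher SEP. Section 7.9, in the paragraph that justifies the sample size for mediation, says "Because evidence of a relationship between SEP and physical activity is mixed", a small-to-medium correlation is hypothesised. It concludes that 400 participants per condition give adequate power for the moderated mediation.

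**Where it is left out.** Section 7.7 first describes the candidate mediators by education: "We will report and compare the measures of inhibition, working memory, healthiness and weight control motivation in food choices overall" and by education level. It then sets a condition: "If the main analyses suggest that highest educational qualification moderates the effect of labelling intervention", mediation analyses follow. The list is explicit: "We will test as mediators the measures of inhibition, working memory, healthiness and weight control motivation in food choices", and only those that differ between education groups. The outcome and hypothesis columns beside the secondary objective in section 2 cover executive function and health motivation only.

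**Where it appears in another role.** Section 5.5 says the IPAQ-SF "will be used to assess the physical activity level", and the study flow in section 6 gives it to all four groups. Section 7.1 derives MET-minutes under its heading for other variables. Section 7.3 reports "physical activity in MET-minutes for vigorous-intensity activity, moderate-intensity activity, walking and in total" by education, with t-tests. Section 7.8 explores whether walking and total MET-minutes "individually moderate the effect of the labelling intervention on self-served energy independently of SEP", at 0.001. The debriefing text in Appendix O tells participants that the study will look at whether more active people made more use of the energy information.

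**The concern.** An objective and the analysis meant to serve it should name the same variables. Here the objective sentence names two mediators, and the mediation section carries forward only one of them, health motivation, together with executive function. If education does change the label effect, the plan as written cannot say whether physical activity accounts for any of that difference, although the data are collected from everyone who completes the study.

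The timing also matters. Section 7.3 uses four MET-minute summaries and section 7.8 uses two, and none is designated for mediation. If the mismatch is noticed only after the results are known, both the decision to test physical activity and the choice of summary would be made with the data in view.

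**Working it through.** This is a question of consistency, so the main check sets the sections side by side.

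| Place | Health motivation | Executive function | Physical activity |
|---|---|---|---|
| Section 2, objective sentence | mediator | not named (general reference to psychological processes) | mediator |
| Section 2, outcome and hypothesis columns | yes | yes | no |
| 7.3 baseline comparison by education | no | no | yes, four MET-minute summaries |
| 7.7 comparison by education | yes | yes | no |
| 7.7 mediator list | yes | yes | **no** |
| 7.8 exploratory moderators, 0.001 | yes | yes | yes, walking and total |
| 7.9 mediation sample-size paragraph | yes, r = 0.17 and r = -0.25 | no | yes, no r given |

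**Could another analysis stand in for the mediation test?** Section 7.7 defines the conditional indirect effect as a × (b1 + b2 × labelling). Here a is the path from education to the mediator, and b1 and b2 describe how the mediator relates to energy under each label.

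- Section 7.3 gives an education difference in MET-minutes, which corresponds to a. It does not involve energy served.
- Section 7.8 puts physical activity in the model in place of education. Its label-by-activity interaction resembles b2, but without education in the model and at 0.001.
- No section forms the product of the two paths for physical activity or gives it a confidence interval.

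**The plan followed as written, in the most favourable case.** Suppose the label-by-education interaction is significant and the t-tests in 7.3 show a clear education difference in MET-minutes. Section 7.7 then runs mediation for whichever of its own listed measures differ by education, and stops. Physical activity is not tested.

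**The figure in 7.9.** 1,600 / 4 = 400 per condition, as stated, which exceeds the approximately 380 taken from a cited source. The path sizes behind 380 are not in the documents, so that figure cannot be reproduced. It does not bear on whether physical activity is on the list.

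**What adding one measure would cost in tests.** For each mediator, section 7.7 plans four conditional indirect effects (one per condition) and three differences from no labelling: 4 + 3 = 7. At the secondary level of 0.01, 7 × 0.01 = 0.07 expected false positives per added mediator, if every condition for testing were met and every null were true. For scale, section 7.1 defines two inhibition measures, two working-memory measures and two motivation scores. If all six were used, the family would be 6 × 7 = 42 tests (0.42 expected). One added measure makes it 7 × 7 = 49 (0.49).

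**The case against.** The strongest reply is that mediation by physical activity was never really intended. Section 2 lists no outcome and no hypothesis for it, section 7.1 files it among other variables, and section 7.9 neither calls it a mediator nor gives a correlation or a path to energy. Appendix O describes a moderation question, and section 7.8 answers that question. On this reading the mediators in 7.7 match the stated hypotheses and only one sentence is out of line.

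Much of this stands, and it makes deletion a genuine remedy. It does not remove the mismatch. The objective sentence is explicit, and the assumption in 7.9 has no evident purpose in a mediation paragraph unless physical activity is a candidate mediator. Appendix O is not decisive either: it describes health motivation in the same terms, and health motivation is a mediator in 7.7. The diagrams in 7.7 are not available in the text reviewed, but the formula refers to a generic mediator and the written list is clear.

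Two stronger readings are tempting, and the documents do not support them:

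- A reader might infer that physical activity is never compared between education groups, because 7.7 leaves it out of its comparison. Section 7.3 makes that comparison, so only the mediation test is missing.
- A reader might infer that the trial is underpowered for this mediation, or that 7.9 should state a detectable difference between conditions. The documents give no correlation for physical activity or executive function and no slopes by condition, so no such figure can be derived for them.

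**Conclusion.** The point holds as an inconsistency between objective and analysis. One of the two mediators named in the objective sentence has no mediation test anywhere in the plan, and neither 7.3 nor 7.8 substitutes for one. Whether the error lies in the objective or in 7.7 cannot be settled from the documents, because section 2 itself points both ways.

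The consequence is limited. The affected analysis is secondary and runs only after a significant label-by-education interaction and an education difference in the mediator. The primary analysis, the sample size and the data collection are untouched. It should be corrected because part of a stated objective would otherwise go unanswered, or be answered by a choice made after the results are known. The conclusion rests on the text alone and needs no numerical assumption.

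**What to change.** Before data are seen, do one of the following.

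1. **Add it.** Put one pre-specified physical-activity measure, for example total or walking MET-minutes, on the mediator list in 7.7. Test it at 0.01 under the same two conditions as the other mediators. The education comparison already planned in 7.3 can serve as its screen; say so in 7.7 and state the level at which it is read, since section 7 does not assign 7.3 to an alpha tier. Complete the outcome and hypothesis columns in section 2 to match. The cost is wording, some bootstrap runs and up to seven more secondary tests, with about 0.07 more expected false positives on the assumptions given above. No new data are needed.
2. **Remove it.** Delete physical activity as a mediator from the objective in section 2 and from the mediation rationale in 7.9, and state that it is examined only as an exploratory moderator in 7.8. This adds no tests. It narrows the objective as now worded, though not the listed hypotheses.

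Either is acceptable; the sponsor should choose according to what was intended. Neither requires a new power statement in 7.9.

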7.8. Exploratory analyses

To account for multiple testing the alpha level for exploratory analyses will be set at $p = 0.001$.

Analysis of potential moderators of the effect of the labelling intervention

We will explore if the other variables we will measure could individually moderate the effect of the labelling intervention on self-served energy independently of SEP. We will substitute highest educational qualification in the main analyses by measures of inhibition, working memory, healthiness and weight control motivation in food choices, physical activity in MET-minutes for walking and in total.

Debriefing questionnaire

Answers to all the items of the debriefing questionnaire will be described as mean \pm SD overall and for participants of lower and higher education. Differences between the two groups will be tested using t-tests. Two ANOVAs will be run to test the effect of the labelling intervention and of highest educational qualification on the first two items: kcal influence and PACE influence.

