7.5. Main analyses

The primary aim of the statistical analyses will be to test the effect the labelling intervention and SEP on self-served energy. Secondary analyses will be run in order to investigate the role of potential mediators to explain the relationship SEP-self-served energy. The measure of SEP used in our main analyses will be the *highest educational qualification* (binary variable: *lower vs. higher*) because previous research showed that people of higher education were more likely to use nutrition labels [35], [36].

² MET-minutes: Metabolic Equivalent of Task of an activity × minutes performed.

Linear mixed effect models will be run in order to test the effect of the labels and of highest educational qualification on the self-served energy, with participants and dishes set as random effects to account for correlation between repeated measures by the same participant and across the different food items. The main model will test the effect of the labelling intervention (four levels: kcal labelling, PACE labelling, kcal and PACE labelling, no labelling), highest educational qualification (two levels: lower, higher) and the interaction between labelling intervention and highest educational qualification. If the interaction is significant, analyses will be stratified by *highest educational qualification (lower and higher)* and two linear mixed models will be fitted to examine the effect of the labelling intervention on self-served energy.

If there is a main effect of the labelling intervention in one of the above linear mixed models we will follow up this main effect by conducting the following pairwise comparisons:

- Self-served energy in each of the three labelling conditions compared to no labelling condition:
 - o No labelling vs. kcal labelling
 - o No labelling vs. PACE labelling
 - o No labelling vs. kcal and PACE labelling combined
- Self-served energy in the combined labelling condition compared to single labelling conditions
 - o Kcal and PACE labelling combined vs. kcal labelling
 - o Kcal and PACE labelling combined vs. PACE labelling
- Self-served energy in one single labelling condition compared to the other single labelling condition:
 - o Kcal labelling vs. PACE labelling

We will apply a Bonferroni correction to the level of significance based on the number of pairwise comparisons made (e.g., 12 comparisons: $0.05/12=0.004$).

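### The exploratory moderator models in section 7.8 drop education, so they cannot show moderation of the label effect independently of SEP; the cost is to interpretation, not to the error rate

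*Combined protocol and SAP*

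**What the plan says.** Section 7.8 sets the aim of exploring whether other measured variables "could individually moderate the effect of the labelling intervention on self-served energy independently of SEP". The next sentence gives the model: "We will substitute highest educational qualification in the main analyses by measures of inhibition, working memory, healthiness and weight control motivation in food choices", with walking and total physical activity also on the list. The alpha for these analyses is 0.001.

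The model being altered is in section 7.5. It has labelling (four levels), "highest educational qualification (two levels: lower, higher) and the interaction between labelling intervention and highest educational qualification", and random effects for participant and dish. Education is the measure of SEP chosen for that model, and no other SEP variable enters it.

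Elsewhere the plan expects these measures to be tied to SEP. Section 2 states that "Participants of higher SEP will have better executive function than participants of lower SEP", and explains the expected stronger label effect in higher SEP by saying that "they will be more motivated by health in their food choices than participants of lower SEP". Section 7.9 reports a "small-to-medium correlation between level of education and healthiness motivation" of r = 0.17 from an earlier study and hypothesises a small-to-medium correlation for physical activity.

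**The concern.** Substitution removes both education and label-by-education. What remains is a label-by-measure term with nothing in the model to separate it from SEP. Randomising the labels does not help here, because the measures are observed characteristics of participants and were not assigned.

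Two things must hold for SEP to enter the label-by-measure estimate: the measure must be associated with SEP, and SEP must modify the label effect. The plan hypothesises both. A significant label-by-motivation term from the substituted model could then partly reflect education, and it could not be described as independent of SEP.

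**Working it through.** The plan gives no power, sample size or estimate for this analysis, so there is no figure to reproduce. The check is whether the model matches the aim and, if it does not, by how much the result could be off.

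**Terms in each model**

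| Model | Label | SEP terms | Measure terms |
|---|---|---|---|
| Main (7.5) | yes | education, label × education | none |
| Substituted (7.8) | yes | none | measure, label × measure |
| Needed for the stated aim | yes | education, label × education | measure, label × measure |

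**Inputs.** From section 7.9: r = 0.17; f = 0.07 for label-by-education; N = 1,600 (400 per arm); SD 300 kcal at each level; 18 dishes per participant. From section 7.8: alpha 0.001. The values r = 0.30 and f = 0.15 used below are assumptions to show a range.

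**Size of the leak.** Suppose the measure M has no moderating effect of its own. Let b_a be the slope of self-served energy on education in arm a, with education and M in SD units and correlated r. Regressing on M alone gives a slope of r × b_a in that arm. The label-by-M contrast against control is therefore r × (b_a − b_control), which is a share r of the label-by-education contrast.

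- At r = 0.17 the share is 17%, and the leaked effect is f = 0.17 × 0.07 = 0.012.
- At an assumed r = 0.30 it is 0.30 × 0.07 = 0.021.

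**Effect on the error rate.** The 3-df label-by-M test has noncentrality of about r² × N × f². At the documented values this is 0.17² × 1,600 × 0.07² = 0.23. Referring it to a noncentral F with 3 and 1,592 df at alpha 0.001 gives:

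| f | r | False-positive rate (nominal 0.001) |
|---|---|---|
| 0.07 | 0.17 | 0.0016 |
| 0.07 | 0.30 (assumed) | 0.0036 |
| 0.15 (assumed) | 0.17 | 0.0053 |
| 0.15 (assumed) | 0.30 (assumed) | 0.030 |

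**Check by simulation.** Participant means were simulated with SD = √(300² + 300²/18) = 308.2 kcal, 400 per arm, 1,500 replicates, no true label-by-M effect, and the same education interaction in all three labelled arms against control.

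| f, r | True label × education, kcal per SD | Label × M, substituted model | Label × M, both education terms kept |
|---|---|---|---|
| 0.07, 0.17 | −49.8 | −8.3 | 0.1 |
| 0.15, 0.30 (assumed) | −106.8 | −32.5 | −0.6 |

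The first row agrees with the algebra: 0.17 × −49.8 = −8.5. In the second row, rejection at 0.001 was 3.4% with the substituted model and 0.13% with both education terms kept. A rate of 0.13% is only 2 of 1,500 replicates, so the analytic table is the better guide to small rates. Keeping both education terms removes the leak.

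**The case against.** **The phrase may mean something looser.** Section 7.7 studies the executive-function and motivation measures only as explanations of an SEP difference. Section 7.8 could then mean only that they are now examined as a separate question, whatever the SEP result. That reading is possible, and on it the model fits and only the wording is at fault. The phrase would still be read by many as a claim of adjustment.

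**Section 7.7 already has an adjusted model.** The moderated mediation takes education as the predictor and lets the effect of each mediator vary with labelling, so label-by-measure is estimated alongside education. This is a real partial answer. However, it runs only if label-by-education is significant and only for measures that differ between education groups. Its inference concerns indirect effects, not the label-by-measure term itself. It also leaves out physical activity. The diagrams are not shown in the text available, so they cannot confirm whether label-by-education is held as well.

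**The numbers are small, and even the base case may be generous.** This stands. The f of 0.07 is the effect the study is said to be able to detect, not one it predicts. The r of 0.17 refers to level of education in another study, while the main model uses a binary split. If the split reduced r by a factor of about 0.8 (an assumption), r would be about 0.14 and the leak about f = 0.010.

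**Inferences the documents do not support.** A reader might infer that the sponsor plans to announce that these measures moderate the label effect independently of SEP. Section 7.8 commits only to exploring the question. A reader might also infer that false positives are materially inflated; at the documented values they are not.

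**Conclusion.** The stated aim and the specified model do not match. The substituted model has no SEP term, so its label-by-measure result is unadjusted for SEP, and nothing elsewhere in the plan fully supplies the adjusted test.

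The consequence is minor and concerns interpretation. At r = 0.17 and f = 0.07 the leak is 17% of the education interaction, f of about 0.012, with a false-positive rate of about 0.0016 against 0.001. It depends on a label-by-education interaction being present and grows with that interaction and with the SEP–measure correlation. The rate of 0.030 needs values that the documents do not give. No correlation is stated for executive function, and section 7.9 calls the evidence for physical activity mixed.

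It is also tempting to say that adding education makes the test independent of SEP. Section 5.2 lists five SEP measures, and binary education captures only part of what they describe. The adjusted result would be independent of education as coded, and no more.

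**What to change.** In section 7.8, add rather than substitute. For each moderator, fit labelling, education and label-by-education, plus the centred measure and label-by-measure, with the same random effects. Describe the label-by-measure test as adjusted for education. Optionally repeat it with equivalised income and with subjective social status in place of education. Report the substituted model beside it, labelled as unadjusted for SEP; unadjusted moderation is a legitimate exploratory question.

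If only the substituted model is kept, delete the words *independently of SEP*.

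The cost is about 4 degrees of freedom per model (1 for education and 3 for label-by-education) out of 1,600 participants, and one extra model per moderator. No new data are needed.
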